6. GENERAL ANALYSIS DEFINITIONS

6.1 TREATMENTS

There are two treatment arms in the study: DE using a dosing algorithm or SOC. The assignment of treatment groups will be based on randomization for randomized patient set as defined in [Section 6.3](#). Patients will be allocated to one of the following treatments given below.

Table 6.1: 1 Labels of treatments for use in the Clinical Trial Report

Treatment	Long label	Short label
A	Dabigatran etexilate	DE
B	Standard of care	SOC

Patients switching from DE to SOC before the end of study will be considered as having treatment periods defined below. Patients switching from the original SOC treatment to another SOC will be considered as no change in the treatment group assignment.

The following periods will be defined:

- Screening: day of informed consent to the day prior to first administration of the trial treatment (DE or SOC)
- On-treatment: day of first administration of trial treatment to last administration of trial treatment + 6 days (residual effect period). This on-treatment period will be used for analysis of safety endpoints and adverse events (AEs), as specified in [Section 7.8.1](#).
- Post-treatment: end of on-treatment period +1 day up to day of the last follow-up visit, lost to follow-up, death, or consent withdraw regarding participation in the trial.
- Post-study: For patients not rolled over to the 1160.108 trial, it starts from last follow-up visit + 1 day up to end of the trial, i.e. the last contact/information received during the trial. For patients rolled over to the 1160.108 trial, it starts from last follow-up visit + 1 day in 1160.106 to the date of informed consent in 1160.108.
- Intention to treat: day of randomization up to Day 84 (+ 7), including all observed time on and off trial medication.
- Full follow-up: day of randomization up to day of the last follow-up visit, lost to follow-up, death, or consent withdrawn regarding participation in the trial.

Please note: for patients who had not reached the end of a treatment period as defined above at EMA interim data cut-off date, the respective treatment period ends at the cut-off date.

The screening, on-treatment, post-treatment, and post-study periods will be used for the summary and listings of AEs. The intention to treat, on-treatment, and full follow-up periods will be used for descriptive and statistical analysis of primary/secondary/further endpoints.

6.2 IMPORTANT PROTOCOL DEVIATIONS

The following table defines the different categories of important protocol deviations (IPDs). The final column describes which IPDs will be used to exclude patients from the different patient analysis sets.

Table 6.2: 1 Important protocol deviations

Category/ Code	Description	Example/Comment	Excluded from
A	Entrance criteria not met		
A1.1	Age \geq 18 years at the time of informed consent / assent	Inclusion criterion 1 not met	None
A1.2	No documented diagnosis of clinically stable VTE per investigator judgment, or not initially treated with parenteral anticoagulation therapy (minimum of 5 to 7 days, but not longer than 21 days)	Inclusion criterion 2 not met	None
A1.3	Anticipated treatment duration with anticoagulants for the VTE episode is less than 3 month, inclusive of the initial parenteral therapy	Inclusion criterion 3 not met	None
A2.1	Patients have conditions associated with an increased risk of bleeding	Exclusion criterion 1 met. Details are specified in the protocol Section 3.3.3	None
A2.2	Renal dysfunction or requirement for dialysis	Exclusion criterion 2 met. Estimated glomerular filtration rate (eGFR) $<$ 60 mL/min/1.73m ² for patients aged 12 to $<$ 18 years or eGFR $<$ 80 mL/min/1.73m ² for patients aged 0 to $<$ 12 years using the Schwartz formula	None
A2.3	Active infective endocarditis	Exclusion criterion 3 met.	None
A2.4	Heart valve prosthesis requiring anticoagulation	Exclusion criterion 4 met.	None
A2.5	Patients with hepatic disease	Exclusion criterion 5 met.	None
A2.6	Pregnant or breast feeding females. Females who have reached menarche and are not using a medically accepted contraceptive method per local guidelines.	Exclusion criterion 6 met.	None
A2.7	Age group 0 to $<$ 2 years with gestational age at birth $<$ 37 weeks or with body weight $<$ 3rd percentile	Exclusion criterion 7 met.	None
A2.8	Anaemia or thrombocytopenia at screening	Exclusion criterion 8 met.	None
A2.9	Prohibited or restricted medication use within one week of the first dose of study medication other than medication for prior VTE treatment and P-glycoprotein inhibitors	Exclusion criterion 9 met.	
A2.10	Patients received an investigational drug in the past 30 days prior to screening	Exclusion criterion 10 met (except patients who have completed the treatment period in 1160.106 trial)	None
A2.11	Allergic / sensitive to any component of the study medication including solvent	Exclusion criterion 11 met.	None
A2.12	Patients or parents / legal guardians considered unreliable to participate in the trial per investigator judgment or any condition which would present a safety hazard to the patient based on investigator judgment	Exclusion criterion 12 met.	None

Table 6.2: 1 Important protocol deviations (cont.)

Category/ Code	Description	Example/Comment	Excluded from	
A	A2.13	Patients or parents/legal guardians who are unwilling or unable to undergo or permit repeat of the baseline imaging tests required to confirm thrombus resolution at study day 84 (or eEOT) or in whom repeating such imaging tests at these pre-specified time points may not be medically in the patient's best interest	Exclusion criterion 13 met.	None
B		Informed consent		
	B1	Informed consent not available/not done	Informed consent date missing	All
	B2	Informed consent too late	Informed consent date was after Visit 1 date	None
C		Trial medication and randomisation		
	C1.1	Incorrect trial medication taken	Medication kit assigned not matching interactive voice response system (IVRS) assignment, not leading to a change in randomized treatment. (e.g. wrong dose or formulation of DE was administered). Wrong dose assigned by investigator.	None
	C1.2	Randomization not followed	Patients not treated according to the randomized treatment, except treatment switched at a later time	None
	C2	Non-compliance	Medication compliance of <80% or >120%. Temporary interruption following protocol specified procedures will not be considered as violation.	None
	C3.1	Incorrect dabigatran titration	A second DE titration was performed after one titration attempt failed, or DE titration was performed when it was not required according to protocol.	None
	C3.2	Dabigatran titration not done when required	DE could have been titrated when the trough DE concentration is outside the 50 to <250 ng/mL range	None
	C3.3	Dabigatran not stopped when plasma trough concentration did not reach therapeutic range after one dose adjustment	Dabigatran not stopped after two confirmed trough concentrations outside 50 to < 250 ng/mL range	None
D		Concomitant medication		
	D1	Prohibited concomitant medication use	Restricted concomitant treatments are listed in protocol Section 4.2.2.1 with appropriate exceptions	None
Z		Other		
	Z1	Patients treated with DE developed renal dysfunction and were not discontinued from DE	Patients with eGFR <50 mL/min/1.73m ² twice on DE and not stopped from DE	None

Table 6.2: 1 Important protocol deviations (cont.)

Category/ Code	Description	Example/Comment	Excluded from
Z2	Patients with observed new thromboembolic event or a clear clinical progression of the baseline VTE and were not discontinued from DE	Patients with new VTE or baseline VTE progression (e.g. based on ISTH guidelines) and not stopped from DE. Details in protocol Section 3.3.4.1.	None
Z3	Patients with drug-related significant/serious AE or drug toxicity and were not discontinued from DE	Patients with drug related significant/serious AE or drug toxicity and not stopped from DE. Details in protocol Section 3.3.4.1.	None
Z4	Patients became pregnant and were not discontinued from DE	Patients become pregnant and not stopped from DE. Details in protocol Section 3.3.4.1.	None
Z5	Patients developed active meningitis, encephalitis, or intracranial abscess and were not discontinued from DE	Patients developing active meningitis, encephalitis or intracranial abscess and NOT stopped from IMP. Details in protocol Section 3.3.4.1.	None

This table includes IPDs checked by both automated SAS program and manual reporting. All manual findings should be reported in manual IPD log for team review during medical quality review meetings (MQRMs) and blinded report planning meetings (BRPMs).

6.3 PATIENT SETS ANALYSED

The patient sets are defined as:

- **Enrolled set:** includes all patients with signed informed consent. The enrolled set will be used for disposition summaries.
- **Randomized set:** This patient set includes all randomized patients in the treatment groups to which they were randomized, regardless of being treated or not.
- **Treated set:** This patient set includes all patients who were dispensed study medication (DE or SOC) and were documented to have taken at least one dose of study medication.
- **Pharmacokinetic set (PKS):** This patient set includes all dabigatran treated patients with at least one evaluable PK measurement and having no protocol deviations relevant to the evaluation of PK endpoints.
- **Pharmacodynamic set (PDS):** This patient set includes all dabigatran treated patients with at least one evaluable PD measurement and having no protocol deviations relevant to the evaluation of PD endpoints.

Summary of patient sets is provided in the following table:

Table 6.3: 1 Patient sets analysed

Class of endpoint	Randomized set	Treated set	PKS, PDS,
Primary efficacy endpoint	Primary analysis	Sensitivity analysis	
Secondary and other endpoints	Components of efficacy endpoint	Selected secondary endpoints	PK, PD related secondary endpoints
Safety endpoints		X	
Demographic/baseline characteristics	X		

Selected secondary endpoints to be analysed on treated set include all secondary endpoints except for components of efficacy endpoint and PK/PD related secondary endpoints.

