5. VARIABLES AND THEIR ASSESSMENT

5.1 EFFICACY - PHARMACODYNAMICS

5.1.1 Endpoints of efficacy

Primary endpoint:

Efficacy combined endpoint Proportion of patients with:

- Complete thrombus resolution and;
- Freedom from recurrent VTE (including symptomatic and asymptomatic, contiguous progression or non-contiguous new thrombus, deep vein thrombosis, pulmonary and paradoxical embolism, thrombus progression) and;
- Freedom from mortality related to VTE.

The events outlined in the above combined primary endpoint will be assessed by radiologists or other such qualified clinicians using an appropriate method such as ultrasound, echocardiography, venography or computed tomography (CT scan) based on the location of the thrombus and the test used to perform the baseline assessment.

All components of the primary efficacy endpoint as well as all bleeding and all fatal events will be centrally adjudicated by an independent blinded committee.

Secondary endpoints:

- Freedom from major bleeding events (MBEs), defined as either fatal bleeding; clinically overt bleeding associated with a decrease in haemoglobin of at least 20 g/L in a 24-hour period; bleeding that is retroperitoneal, pulmonary, intracranial or otherwise involves the central nervous system; or bleeding that requires intervention in an operating suite.
- Pharmacokinetic and pharmacodynamic assessments at visit 3 (after at least six consecutive dabigatran doses) and after at least 3 days following any dabigatran dose adjustment
- Frequency of dose adjustments (i.e. Number of subjects with dose adjustment), temporary and permanent discontinuation from therapy and number of subjects with laboratory monitoring requirements for dose adjustment during the treatment phase
- Frequency of switch of type of anti-coagulation therapy (including dabigatran to SOC) (Frequency of subjects switching the type of anti-coagulation therapy including dabigatran etexilate to standard of care and switching from an intended standard of care treatment to another)
- Freedom from thrombus progression at end of therapy (day 84 after randomisation (Visit 8) or eEOT whichever comes first) compared to baseline
- Assessment of the acceptability of an age-appropriate formulation at end of therapy
- All bleeding events

Proprietary confidential information.

© 2019 Boehringer Ingelheim International GmbH or one or more of its affiliated companies. All rights reserved.

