7.3.1 Primary analyses

The primary efficacy endpoint, proportion of patients with complete thrombus resolution and freedom from recurrent VTE or mortality related to VTE, will be analysed following the ITT principle on the randomized set. Age group will be used as stratification factor using a Mantel-Haenszel type weighted average of differences with weights as proposed by Greenland and Robins ([R09-1299](#)).

The primary analyses for primary endpoints will include only adjudicated events.

The planned analyses are summarized in Table 7.3.1: 1 for each population set. More details and additional analyses will be specified in TSAP if deemed necessary.

Table 7.3.1: 1 Summary of planned analyses

Population / analysis	Intent-to-treat analysis (from randomization to the time point of interest)	On-treatment analysis (from treatment start to drug stop date + 6 days)
Randomized set	1. Primary efficacy endpoint: primary and secondary analysis 2. Secondary efficacy endpoints 4. All cause mortality	
Treated set		1. Major bleeding events analysis 4. All cause mortality

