7.3.3 Safety analyses

Major bleeding events will be analysed as a secondary endpoint. All bleeding events and combined endpoint of major and clinical-relevant bleeding events will be analysed by the Cox proportional hazards model with treatment being the factor and stratified by age group if appropriate. Pooling of age groups or non-stratified analysis might be performed if the event rate is low. All safety analyses as well as all bleeding events and all-cause mortality analysed as efficacy endpoints will be performed on the treated set.

The safety analysis set will include all randomized patients who take at least one dose of study medication. Patients in the safety population will be analysed according to the study treatment they have received. The safety analyses will be descriptive in nature and will be based on BI standards. The safety analyses will include the following parameters:

- All AEs
- protocol-specified AESI
- serious AEs
- AEs leading to treatment discontinuation

AEs will be coded using the MedDRA dictionary. All AEs will be classified according to the following trial periods: screening, on-treatment, post treatment. All AEs with an onset date/time after the 1st dose of trial medication up to 6 days after the last intake of study medication will be assigned to the treatment period for evaluation. In addition, AEs with onset date before start of the trial treatment but with worsening in intensity during the treatment will also be assigned to the on-treatment period. Other AEs will be assigned to the screening or post-treatment period, respectively. All AEs (including bleeding) in the treatment period will be tabulated in total and according to seriousness, severity and possible relationship to trial medication. AEs in the screening or follow-up period will be listed.

Other lab data, vital signs, physical examinations data and ECG data will be reported descriptively.

Proprietary confidential information.

© 2019 Boehringer Ingelheim International GmbH or one or more of its affiliated companies. All rights reserved.

This document may not - in full or in part - be passed on, reproduced, published or otherwise used without prior written permission.

Proprietary confidential information.

© 2019 Boehringer Ingelheim International GmbH or one or more of its affiliated companies. All rights reserved.

This document may not - in full or in part - be passed on, reproduced, published or otherwise used without prior written permission.

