Permanent discontinuation from therapy and the reasons will be summarized in the disposition table.

Assessment of acceptability

Assessment of acceptability of an age-appropriate formulation at the end of therapy will be provided descriptively for DE treated patients.

Assessment of acceptability of capsules, pellets and OLF reconstituted with flavoured or unflavoured solvent at Days 3 (Visit 3), 21 (Visit 5) and 84 (Visit 8), or eEOT after randomisation will be summarized descriptively as well. Questions completed by investigator, by parent/legal guardian, and by patients (if old enough per investigator judgement) will be summarized descriptively.

Thrombus progression

Frequency of patients free from thrombus progression at day 84 ± 7 days after randomization (or eEOT, whichever comes first) will be analyzed descriptively by treatment arm and age group. Patients without VTE assessments by this time point will be summarized as well. Mortality related to VTE will be considered as recurrence of VTE.

All bleeding events and all-cause mortality

All adjudicated bleeding events and adjudicated all-cause mortality will be analyzed as time-to-event endpoint using stratified Cox proportional hazard model with treatment as a covariate in the model and age group as the stratification factor. A pooling of age groups might be necessary if no events were observed in certain age group.

Patients that do not experience any bleeding events will be included as censored observations at the date of patients' last visit, the date of death not related to bleeding, or the date of data cut-off, whichever comes first. Patients being alive at the end of observational period will be censored for all-cause mortality at the date of patients' last date known to be alive, or the date of data cut-off whichever comes first. All bleeding events and all-cause mortality based on treated set will be analysed descriptively and by Kaplan-Meier estimates for each treatment arm.

Incidence of bleeding events including MBEs, CRNM, minor bleeding events, and any bleeding events will be presented, as well as incidence of combined endpoint of major and CRNM bleeding events.

Components of efficacy endpoint

All components of the primary endpoint will be analyzed as proportions using adjudicated data as the primary analysis in [Section 7.4](#). Concordance between adjudicated events and investigator-reported events will also be summarized.

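### The SAP drops, without saying so, the protocol table's randomised-set analyses of all-cause mortality and thrombus progression, and the protocol contradicts itself on the set for mortality

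*SAP*

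**What the plan says.** Protocol Table 7.3.1:1 crosses analysis set with follow-up period. For the randomised set under intention to treat it lists, after the primary endpoint, "2. Secondary efficacy endpoints 4. All cause mortality". For the treated set under on-treatment follow-up it lists "1. Major bleeding events analysis 4. All cause mortality". Mortality is thus planned twice.

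Protocol 5.1.1, which defines the efficacy endpoints, includes among the secondary ones "Freedom from thrombus progression at end of therapy (day 84 after randomisation (Visit 8) or eEOT whichever comes first) compared to baseline". Protocol 7.3.2 makes that analysis descriptive and names no analysis set. Protocol 7.3.3 then says: "All safety analyses as well as all bleeding events and all-cause mortality analysed as efficacy endpoints will be performed on the treated set".

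SAP 6.3 states: "Selected secondary endpoints to be analysed on treated set include all secondary endpoints except for components of efficacy endpoint", and it excepts the PK/PD endpoints as well. In SAP 7.5.2 mortality has an age-stratified Cox model, with no set named in that sentence, and afterwards "all-cause mortality based on treated set will be analysed descriptively and by Kaplan-Meier estimates for each treatment arm". Thrombus progression is described by arm and age group, again with no set named. SAP Section 4 mentions only the change to major bleeding and otherwise points to the protocol amendments.

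**The concern.** The treated set excludes patients after randomisation. The trial is open-label, so a family or investigator knows the allocation before the first dose, and the reasons for never starting treatment can differ by arm. For mortality in particular, the comparison of patients as randomised is the one that is protected against this. The protocol's table planned it, and the design collects the data by following patients after they stop study medication.

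The period matters as well. Protocol 7.3 ends treated-set events six days after the last dose when treatment stops early. Several events require a dabigatran patient to stop, whereas a SOC patient who changes to another type of SOC still counts as on treatment (protocol 4.1.4 and 6.2.3). If that window were applied to mortality, observation would tend to end earlier in the dabigatran arm, often for reasons related to prognosis.

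**Working it through.** No arithmetic applies to the main point, so the check sets the texts side by side.

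| Endpoint | Protocol Table 7.3.1:1 | Protocol text | SAP |
|---|---|---|---|
| All-cause mortality | Randomised set, ITT; also treated set, on-treatment | 7.3.3: treated set | 6.3 and 7.5.2: treated set |
| Freedom from thrombus progression | Randomised set, ITT (as a secondary efficacy endpoint) | 7.3.2: descriptive, no set named | 6.3: treated set by the general rule; 7.5.2: no set named |
| Components of the primary endpoint | Randomised set, ITT (as secondary efficacy endpoints) | 7.3.2: same model as the primary analysis | 6.3: randomised set |

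1. **Mortality.** The table gives two analyses and 7.3.3 gives one. The two protocol passages disagree, and the SAP adopts 7.3.3. What is lost is the table's ITT entry.

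2. **Progression.** Protocol 7.3.2 is silent on the set, so the table's entry for secondary efficacy endpoints is the only assignment in the protocol. SAP 6.3 departs from it.

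3. **Declaration.** SAP Section 4 reports no change of analysis set. The SAP history entry for 6.3 mentions added sets, revised set definitions and removal of the co-primary safety endpoint, but not this change. The amendment descriptions available in the protocol do not mention it either.

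4. **Period for mortality.** Protocol 7.3 closes the treated-set window at Visit 8, or at last dose + 6 days after early discontinuation. SAP 7.5.2 censors survivors at the last date known alive or at data cut-off, whichever is earlier. SAP 6.1 makes the ITT, on-treatment and full follow-up periods all available for secondary endpoints without assigning them. SAP 7.8 ties safety analyses to the on-treatment period. No sentence says which period governs mortality.

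5. **Size.** The difference in deaths between the two analyses can be written as

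   deaths (randomised set, ITT) − deaths (treated set) = deaths in never-dosed patients + deaths after last dose + 6 days and within the ITT period,

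   where the second term arises only if the on-treatment window is used. The documents give neither term. For progression only never-dosed patients can matter, because the endpoint closes at the early end-of-treatment visit whichever set is used.

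**The case against.** The strongest reply is that the SAP follows the protocol on mortality. Protocol 7.3.3 assigns it to the treated set even when it is treated as an efficacy endpoint, and the table lists it there too. This stands. A reader might infer that the SAP moved mortality away from the protocol's only plan. The documents do not support that: the protocol disagrees with itself, and the SAP keeps one half without noting that the other is dropped.

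A reader might also infer that deaths after dabigatran is stopped will be lost. That is not established. The censoring rule in SAP 7.5.2 points towards longer follow-up, so the fair statement is that the period is ambiguous.

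On progression, the reply is that little is at stake. The analysis is descriptive and its time point is fixed. Thrombus progression is also counted in the recurrent-VTE component of the primary endpoint, which stays on the randomised set up to Day 84 + 7. This stands too, and it limits the impact. Randomisation and first dispensing are both at Visit 2, so never-dosed patients may be few.

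It is tempting to size the problem from the paediatric LMWH trial in protocol 1.1, which had 5 deaths in 76 patients: 5/76 × 141 = 9.3 deaths. Its two arms taken separately give 1/36 × 141 = 3.9 and 4/40 × 141 = 14.1. These are crude totals of deaths, not the number that a change of set or window would move, and they cannot serve as its size.

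Finally, the public text is incomplete. Numbering skips item 3 in the protocol table and sections 6.4 and 7.6 in the SAP, so a supplementary mortality output might exist there. That tempers any claim that ITT mortality is wholly absent. It does not alter the explicit rule in SAP 6.3.

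**Conclusion.** The point holds in a limited form. The protocol is inconsistent on the analysis set for all-cause mortality. The SAP retains only the treated-set version, places thrombus progression on the treated set through a general rule, and declares neither. The mortality period is left open.

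The effect cannot be quantified from the documents. For progression it is small. The primary conclusion is unaffected, since the primary endpoint and its components stay on the randomised set. The case for acting is that the planned as-randomised analysis can be restored cheaply and that doing so removes an avoidable post-randomisation exclusion in an open-label trial. The verdict assumes that the table governs progression, where the protocol text names no set, and that the missing SAP sections do not override the rule in 6.3.

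**What to change.** - In SAP Table 6.3:1 and 7.5.2, analyse all-cause mortality on the randomised set with patients as randomised, over the ITT period to Day 84 + 7 and over full follow-up. Keep on-treatment mortality in the treated set as supportive, and state the period and censoring rule for each analysis.
- Present freedom from thrombus progression on the randomised set. Keep its defined time point, Day 84 or the early end-of-treatment visit, whichever comes first. Extending it to Day 84 + 7 regardless of early stopping would change the endpoint. SAP 7.5.2 already counts patients without an assessment, so never-dosed patients can be shown there.
- Reconcile protocol 7.3.3 with Table 7.3.1:1. If any randomised-set analysis is still to be omitted, declare and justify that in SAP Section 4.

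The cost is wording and one or two additional tables. The protocol already plans to collect the data needed.
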